There is a difference between ultrasound guided Pericapsular Nerve Group Block and ultrasound guided Fascia Iliaca Block as a regional analgesic techniques for pre- and post-operative analgesia in elderly patients with hip fracture.

Aim of the work

The aim of the present study is to improve quality of pain control in the pre- and post-operative periods in elderly patients with hip fracture.

Objectives

1. To compare the time of performance and the analgesic effect in the pre- and post-operative periods between ultrasound guided Pericapsular Nerve Group (PENG) block, fascia iliaca block and intravenous fentanyl (control group).
2. To assess the quality of patient's positioning during performance of spinal anesthesia by operator satisfaction score.
3. To assess time of onset of postoperative ambulation.

Patients and Methods

I. Technical design:

● **Site of the study:**

This study will take place at Zagazig University Hospitals after approval of Institutional Review Board (IRB).

● **Duration of the study:**

Two years.

● **Sample size:**

Assuming that mean \pm SD for VAS scores at positioning for spinal anesthesia in intravenous fentanyl versus fascia iliaca block were 3.5 ± 2.5 versus 2.1 ± 0.9 [4] with confidence level 95% and power of test 80%.

The total sample size is 51 (17 in each group) calculated by OpenEpi[®].

● **Inclusion criteria:**

1. Patient acceptance.
2. Accepted mental state of the patient.
3. Gender: both sexes.
4. Age above 65 years old.
5. Body mass index 18.5-35 kg/m².
6. ASA physical status II and III.
7. Unilateral hip fracture assigned for surgical fixation.
8. Expected duration of surgery \leq 3 hours.

● **Exclusion criteria:**

1. Associated trauma or multiple fractures.
2. Peripheral neuropathy.
3. Coagulopathy.
4. Infection at site of injection.
5. Allergy to the drugs used in the study.
6. Advanced kidney, liver or heart disease.

- **Withdrawal criteria:**

The patient has the right to withdraw from the study at any time without any negative consequences on their medical or surgical treatment plan.

II. Operational design:

- **Type of the study:**

This study is a randomized double-blind controlled clinical trial.

- **Parameters of the study:**

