Fascia Iliaca block group (n=17): Patients will be assigned to receive Fascia Iliaca Block (F.I Block) before positioning for spinal anesthesia.

After disinfection of the skin over the upper thigh with alcohol on the affected side, sterile drapes will be used to surround the area of the block. While the patient in the supine position, a linear high-frequency ultrasound probe (10–15MHz) will be placed in the inguinal crease to identify the femoral artery and vein in the short axis. Then the ultrasound probe will be slid laterally while identifying the psoas muscle until the most anterior position of the curve of the psoas muscle is identified. A 22-gauge, 80-mm needle is inserted and advanced using an in-plane technique until the tip of the needle is positioned at that point, noting the ‘pop’ through the fascia lata and fascia iliaca. A small test injection is made to ensure that the fluid is seen to lift the fascia iliaca and flow between the fascia and the psoas muscle. After negative aspiration, 30 mL of 0.25% bupivacaine + 250 mg magnesium sulphate is injected in 5 mL increments under ultrasound visualization, with repeating test aspiration after every 5 mL. An expanding anechoic collection just below the fascia iliaca separating it from the psoas muscle should be certainly visualized indicating correct placement of anesthetic solution [17].

In the three groups, the onset of analgesia will be detected by 15 degrees leg raising test and will be recorded. The 15 degrees leg raising test will be used after 10 minutes from injection of local anesthetic in the groups received regional analgesia and after 2 minutes from intravenous injection in the fentanyl group. While the patient is supine, we will try to passively elevate the patient’s leg on the affected side for 15 degrees. If the patient complains of intolerable pain on moving his leg, the test will be aborted and we will wait for a minute before repeating the test. The test will be repeated every minute until we detect the onset of the analgesia that will be represented by dynamic VAS ≤ 4 . For all patients visual analogue pain

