score (VAS) is used to evaluate pain. VAS is done by drawing a 10cm vertical line on a piece of paper with its limits “no pain” (0) on one side and “extreme pain” (10) on the other side. The patient will be asked to point where the pain (he/she) experiences lies on the line and the score is recorded ^[18]. Patient will be asked to evaluate his pain on VAS scale before and after the analgesic technique (starting 10 minutes after regional blocks and repeated every minute and 2 minutes after fentanyl injection). Once $VAS \leq 4$, patient will be positioned to receive spinal anesthesia. Vital signs will be recorded with each VAS reading.

Administration of spinal anesthesia:

After analgesia is established and fluid preload is given, patient’s position will be changed to sitting position to receive spinal anesthesia. Spinal anesthesia will be administered by an anesthesiologist who is blinded to groups’ assignment.

Anesthesiologist’s satisfaction with patient’s positioning will be evaluated by operator satisfaction score ; 0=unsatisfactory, 1=satisfactory, 2=good or 3=optimal ^[4]. This scoring will be done by the anesthesiologist responsible for spinal anesthesia administration.

During patient positioning for spinal anesthesia, VAS and vital signs (HR, MAP, SpO₂ and body temperature) will be recorded. If a patient reports $VAS \geq 4$ during positioning, the procedure will be stopped, the patient will be recorded as a failure rate and 1 mic/kg of i.v. fentanyl will be administered in any group. Positioning will be reattempted after VAS is reduced to <4.

After patient is in the sitting position, sterilization of the skin of the back will be done by 10% betadine then sterile drapes are used to surround the area of injection. Then 2 cc of 2% lidocaine will be injected to anesthetize the skin and subcutaneous tissue by forming a skin wheel. Spinal anesthesia will be performed by paramedian approach in the intervertebral space (L3/L4) using a 25G Quincke spinal needle with the bevel directed laterally. After correct needle placement in the subarachnoid space which is confirmed by free flow of cerebrospinal fluid (CSF), 2.5 cc of 0.5% hyperbaric bupivacaine (12.5 mg) + 25 mic fentanyl will be

injected in the subarachnoid space and the needle will be extracted. The skin will be dressed and the patient will be placed in the supine position and oxygen will be supplied by a facemask.

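### Positioning VAS, on which the trial is sized, is read only after every patient has been brought to VAS ≤4, so group differences in it are compressed and a null result there does not show equal analgesia

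*Protocol*

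**What the plan says.** Protocol, Sample size: the only variable used for sizing is pain at positioning. The assumption is "VAS scores at positioning for spinal anesthesia in intravenous fentanyl versus fascia iliaca block were 3.5 ± 2.5 versus 2.1 ± 0.9", "with confidence level 95% and power of test 80"%, giving 17 per group and 51 in total.

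Protocol, Operational design, end of the Group F text: in all three groups a passive 15-degree leg raise is tried, first at 10 minutes after a block or 2 minutes after fentanyl. "The test will be repeated every minute until we detect the onset of the analgesia", with onset defined as dynamic VAS ≤4. No time limit is given. The VAS schedule for the block groups is described in the same way: "starting 10 minutes after regional blocks and repeated every minute". Once VAS is ≤4, the "patient will be positioned to receive spinal anesthesia".

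Protocol, Administration of spinal anesthesia: VAS is recorded during positioning. At VAS ≥4 the attempt stops, the patient is counted as a failure, intravenous fentanyl is given in any group, and positioning is tried again only when VAS is below 4. The text does not say whether the first or the repeat reading is the positioning VAS.

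Protocol, Collecting data: onset time to VAS ≤4 and VAS before and after the technique are also collected.

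**The concern.** The sized variable is read after a rule that treats every patient, by waiting, to the same pain threshold. A slower or weaker technique then shows up partly as a longer wait and less as a higher score at positioning. The second rule (fentanyl in any group, repeat below 4) draws the groups together again if the repeat reading is the one analysed.

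Two things are at stake. First, similar positioning scores could be read as equal pre-operative analgesia when they partly reflect titration to a common target. Second, the 80% power statement is attached to a reading whose group difference the procedure itself reduces. Analysis of the positioning scores alone cannot recover that loss.

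**Working it through.** **Inputs.** From Sample size: fentanyl 3.5 (SD 2.5), fascia iliaca 2.1 (SD 0.9), 17 per group, 95% confidence (two-sided 0.05 assumed), power 80%. From Operational design: threshold 4. Not in the protocol, and therefore assumed: normal scores, the same mean and SD for leg-raise and positioning VAS within each group, and the correlation ρ between them.

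**Step 1: the plan's own figure.** n per group = (SD₁² + SD₂²)(z₀.₉₇₅ + z₀.₈₀)²/δ² = (6.25 + 0.81)(1.960 + 0.842)²/1.4² = 28.3, so 29 per group. The stated 17 is not reproduced. At 17 per group, power is Φ(1.4/√(7.06/17) − 1.960) = 58% by normal approximation and about 54% by simulated Welch test. This shortfall exists before any waiting rule and is a separate sample-size defect.

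**Step 2: where the rule acts.** P(VAS > 4) is 1 − Φ((4 − 3.5)/2.5) = 1 − Φ(0.20) = 42% for fentanyl and 1 − Φ((4 − 2.1)/0.9) = 1 − Φ(2.11) = 1.7% for fascia iliaca. The wait therefore falls almost wholly on the fentanyl arm.

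**Step 3: effect on the difference.** Let a leg-raise score X above 4 be held until it reaches 4, and let positioning VAS = m + ρ(min(X, 4) − m) + √(1 − ρ²)·SD·e, with e standard normal. The mean reduction is ρ·E[(X − 4)⁺], where E[(X − 4)⁺] = SD[φ(k) − k(1 − Φ(k))] and k = (4 − m)/SD.
- Fentanyl: 2.5 × (0.391 − 0.20 × 0.421) = 0.77.
- Fascia iliaca: 0.9 × (0.0430 − 2.11 × 0.0174) = 0.006.

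The difference is thus about 1.4 − 0.76ρ. Limiting scores to 0-10 raises the fentanyl mean and adds a little under 0.1.

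**Step 4: simulation** with scores limited to 0-10, Welch test, 17 per group. Differences are good to about 0.01 and power to about 1 percentage point.

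| ρ (assumed) | Difference | Power | First positioning VAS ≥4: fentanyl / fascia iliaca |
|---|---|---|---|
| 0 | 1.48 | 65% | 42% / 1.7% |
| 0.3 | 1.27 | 53% | 38% / 1.7% |
| 0.5 | 1.11 | 46% | 35% / 1.7% |
| 0.7 | 0.96 | 41% | 32% / 1.6% |
| 0.9 | 0.80 | 40% | 27% / 1.3% |

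Power levels off near 40% because the fentanyl SD shrinks together with the difference (2.32 at ρ = 0, 1.62 at ρ = 0.9). The last column shows that failure at first positioning still separates the groups under these inputs.

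The right comparator for the loss is the 65% in the first row, which uses the same 0-10 limit. The 54% from the unrestricted inputs belongs to Step 1.

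**The case against.** The strongest reply is that the gated score and the sized score are different readings. The wait applies to a supine passive leg raise, whereas the sized score is taken during the move to sitting. The protocol itself provides for VAS ≥4 during positioning, so a first positioning score is not capped at 4. This stands. A reader might infer that the rule hides the pre-operative difference altogether, or that it should be modelled by truncating scores at 4 (means 2.29 and 2.08, difference 0.2, power about 10%). The documents do not support either. Holding patients exactly at 4 with both readings identical (difference 0.73, power about 42%) is likewise a limiting case.

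Second, the planning figures come from a cited study, and the protocol does not say whether that study also waited for analgesia before positioning. If it did, applying the wait again counts it twice. This also stands, so it cannot be said that the procedure is unable to produce a 1.4-point difference. It does not rescue the 80%, which the printed inputs fail to give at 17 per group in any case.

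Third, onset time, VAS after the technique and failures are recorded and can carry the difference, and the protocol does not name positioning VAS as its sole or primary outcome. That is correct, and it is why the fix needs no new data. It does not change how a null result on positioning VAS should be read.

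**Conclusion.** The point holds as compression, not removal. The order of events is explicit: every patient is brought to leg-raise VAS ≤4 before the sized variable is read, and a second rule acts on those who reach 4 or more during positioning. Part of any group difference moves into onset time and the failure count, so a null result at positioning is not evidence of equal analgesia.

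On the printed inputs the loss is from about 1.5 to between 1.3 and 0.8 points, and from about 65% to between 53% and 40% power, for ρ from 0.3 to 0.9; it is nil at ρ = 0. The direction for any positive correlation follows from the procedure. The size rests on the normal model, on equal means and SDs for the two readings, on the assumed ρ, and on planning scores that do not already include such a wait. The figures concern fentanyl versus fascia iliaca only, since the protocol gives no planning values for PENG.

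Separately, a patient at exactly VAS = 4 satisfies the rule for positioning and also meets the definition of failure during it. These passages contradict each other and must be reconciled; which threshold is right is not judged here.

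**What to change.** No dose, threshold or treatment rule needs to change for the statistical correction.

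1. Do not attach the 80% power statement to positioning VAS.
2. For PENG versus fascia iliaca, pre-specify the first leg-raise VAS at 10 minutes as a pre-operative pain comparison. It is already recorded, at the same time in both block groups and before anyone is held back. Give a test aborted for intolerable pain the worst rank and use a rank-based comparison. State that this score reflects speed of onset as well as depth of analgesia.
3. For comparisons with fentanyl, where the first test is at 2 minutes and the 10-minute score is no common yardstick, report onset time and failure at first positioning beside positioning VAS.
4. Define positioning VAS as the first reading, before any fentanyl given for failure, and describe it as pain in patients already brought to VAS ≤4.
5. Reconcile the ≤4 positioning rule with the ≥4 failure rule at VAS = 4, and define failure accordingly.

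The cost is protocol wording, with no new measurement. The price in claims is that positioning VAS loses its stated power, and the 10-minute comparison has no sample-size basis in the protocol. Its precision at 17 per group should be reported as it is, or it should be sized on its own assumptions.

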- In the elderly parenteral fentanyl may cause delirium or respiratory depression. Delirium can be assessed using the confusion assessment method (CAM). The CAM diagnostic algorithm is based on four cardinal features of delirium: 1) acute onset and fluctuating course, 2) inattention, 3) disorganized thinking, and 4) altered level of consciousness. A diagnosis of delirium according to the CAM requires the presence of features 1, 2, and either 3 or 4 [20].

At the end of the procedure patient will be asked to evaluate the analgesic technique used by patient's satisfaction score: Patient will be asked to rate his satisfaction with the technique of analgesia used by giving a score on a 1-3 scale (1 = unsatisfactory analgesia, 2 = satisfactory analgesia, 3 = excellent analgesia) [21].

In the recovery room: Patient will receive 1 gm paracetamol and 30 mg ketorolac by intravenous infusion as a part of standard multimodal analgesia.

In the ward: Postoperative standard analgesia will continue in the form of 1gm paracetamol/8hours and ketorolac 30 mg/12hours. Patient will be monitored for vital signs (HR, MAP, SpO₂ and body temperature), time of offset of spinal anesthesia (time from end of intrathecal injection of hyperbaric bupivacaine till recovery of the lower limbs motor power indicated by achieving grade 0 on modified bromage scale and fine touch sensation indicated by sensing pin brick) and postoperative pain by VAS score. Vital signs and VAS will be recorded at 2, 4, 6, 12 and 24 hours postoperative.

If patient gives VAS \geq 4 or complains of intolerable pain, a rescue analgesia will be given in the form of nalbuphine 0.1 mg/kg. We will record time of first rescue analgesia (the time between complete injection of the local anesthetic in the regional groups or fentanyl injection and the first analgesia requested by the patient), total postoperative rescue analgesic consumption in first 24 hours and time of onset of postoperative ambulation.

• **Collecting data:**

From each patient the following data will be collected:

- Patient characteristics (name, age, gender, body mass index (BMI), ASA grade).
- Fracture type.
- Type and duration of surgery (time from end of skin preparation till suturing the wound).

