- Physical examination (mental status, decubitus, chest, abdomen, neurological and examination of the site of injection), laboratory investigations (complete blood count, random blood sugar, international normalized ratio, prothrombin time, partial thromboplastin time, kidney functions tests, liver functions tests and serum electrolytes).
- Vital signs (heart rate, mean blood pressure, respiratory rate, temperature and SpO₂). Vital signs will be recorded before and after the analgesic technique, during positioning for spinal anesthesia and then every 10 minutes till the end of the surgery. Then we will record vital signs at 2, 4, 6, 12 and 24 hours postoperative.
- Intraoperative total fluids given, blood loss and urine output.
- Visual analogue pain score will be recorded before and after analgesic technique used (starting 10 minutes after regional blocks and repeated every minute and 2 minutes after fentanyl injection) and during positioning. VAS will be also recorded at 2, 4, 6, 12 and 24 hours postoperative.
- Time of block performance (time from the end of skin sterilization till end of injection of local anesthetic).
- Onset time of the analgesic technique (time from end of injection of local anesthetic or intravenous fentanyl till reaching VAS \leq 4) by 15 degrees leg raising test. The 15 degrees leg raising test will be used after 10 minutes in the groups received regional analgesia and 2 minutes in the fentanyl group. We will try to elevate the patient's leg for 15 degrees. If the patient complains of pain on moving his leg, the test will be aborted and we will wait for a minute before repeating the test.
- Patient's satisfaction score.
- Anesthesiologist satisfaction score for patient's positioning.
- Possible complications of spinal anesthesia, regional blocks and parenteral fentanyl.

- Time of first rescue analgesia (the time between complete injection of the local anesthetic in the regional groups or fentanyl injection and the first analgesia requested by the patient) and total postoperative rescue analgesic consumption in first 24 hours postoperative.
- Time of onset of postoperative ambulation (time from end of surgery till first ambulation by the patient).
- Duration of spinal anesthesia (time from end of injection of intrathecal hyperbaric bupivacaine till offset of spinal anesthesia effect detected by degree 0 on modified bromage score and return of fine touch detected by sensing pin bricks).

- **Statistical analysis:**

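### A VAS of exactly 4 permits the first positioning attempt, but during positioning it is a failure needing rescue fentanyl, and it bars a reattempt

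*Protocol*

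**What the plan says.** All the rules are in the Protocol under II. Operational design.

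- **Onset.** In the leg-raise paragraph after the Group F description: "The test will be repeated every minute until we detect the onset of the analgesia that will be represented by dynamic VAS" ≤ 4. Collecting data repeats the cut-off: "Onset time of the analgesic technique (time from end of injection of local anesthetic or intravenous fentanyl till reaching VAS" ≤ 4.
- **First positioning.** In the VAS paragraph just before Administration of spinal anesthesia, once VAS is ≤ 4 the "patient will be positioned to receive spinal anesthesia".
- **Failure during positioning.** In Administration of spinal anesthesia, if VAS is ≥ 4 while the patient is being positioned, "the procedure will be stopped, the patient will be recorded as a failure rate and 1 mic/kg of i.v. fentanyl will be administered", whatever the group.
- **Reattempt.** In the same paragraph: "Positioning will be reattempted after VAS is reduced to <4".
- **Reading the scale.** The VAS is a 10 cm line. "The patient will be asked to point where the pain (he/she) experiences lies on the line and the score is recorded"; the precision of that reading is not given.

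On the ward, VAS ≥ 4 also triggers rescue, with a different drug (nalbuphine).

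**The concern.** The set of scores that allows the move (≤ 4) and the set that stops it (≥ 4) share the value 4. A patient may be moved at a score that already meets the stop rule, so the entry gate leaves no margin at that value. In addition, the first attempt and the reattempt are the same move to sitting, yet one is allowed at 4 and the other is not, with no reason given.

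These are bedside rules that decide whether an elderly patient receives another opioid dose and whether the technique is counted as failed. For a patient at an unchanged 4, the protocol records an onset time and then a failure on the same score. The general risks of rescue fentanyl belong to the rescue rule and apply to every rescued patient. The overlap adds only those at exactly 4.

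**Working it through.** **Step 1. Compare the rules at three scores**

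| Rule | VAS 3 | VAS 4 | VAS 5 |
|---|---|---|---|
| Onset reached (≤ 4) | yes | yes | no |
| First positioning allowed (≤ 4) | yes | yes | no |
| Failure and fentanyl during positioning (≥ 4) | no | yes | yes |
| Reattempt allowed (< 4) | yes | no | no |

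At 3 and at 5 the four rules agree. They disagree only at 4.

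**Step 2. Order of size**

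The protocol states no figure for this, so there is none to reproduce. The only inputs available are the Sample size planning values, which describe "VAS scores at positioning for spinal anesthesia in intravenous fentanyl versus fascia iliaca block were" 3.5 ± 2.5 and 2.1 ± 0.9. There are 17 patients per group. No planning values are given for the PENG group.

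Assumptions: scores are normal; the positioning values are borrowed for the entry gate; all 17 patients per group pass the gate; the line is read in steps of w cm.

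Share at exactly 4 among scores at or below 4 = [Φ((4 + w/2 − m)/s) − Φ((4 − w/2 − m)/s)] / Φ((4 + w/2 − m)/s)

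Millimetre reading, w = 0.1:

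- Fentanyl (m = 3.5, s = 2.5): 0.0156 / Φ(0.22) = 0.0156 / 0.587 = 0.027; × 17 = 0.45 patients.
- Fascia iliaca (m = 2.1, s = 0.9): 0.0048 / Φ(2.17) = 0.0048 / 0.985 = 0.0049; × 17 = 0.08 patients.

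Whole-number reading, w = 1:

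- Fentanyl: 0.155 / Φ(0.40) = 0.155 / 0.655 = 0.237; × 17 = 4.0 patients.
- Fascia iliaca: 0.0561 / Φ(2.67) = 0.0561 / 0.996 = 0.056; × 17 = 0.96 patients.

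The fentanyl model puts some probability below zero. Excluding it raises the fentanyl counts to 0.52 and 4.4; fascia iliaca is unchanged.

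**Step 3. What these counts can bear**

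Within the model they are ceilings on the extra failures, because a patient at 4 on entry is affected only if the score is still 4 when moved. A rise above 4 is a failure under any version of the rule.

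The model does not describe the gate well, however. The leg raise is repeated each minute and stops at the first score that passes, so entry scores are first-crossing values and not a truncated sample of positioning scores. The true share could be lower or higher. The whole-number results show only that the answer depends on an unstated reading precision.

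**The case against.** The strongest reply is that the rules apply one after the other. The ≤ 4 rule is read with the patient supine, at a 15-degree leg raise. The ≥ 4 rule is read later, during the move to sitting. Ready to try, then stop if it hurts, is a workable sequence, and a stricter gate after a failed attempt is not a contradiction in itself. This stands in part: staff never face two opposite orders at one moment, and failure after pain rises on moving is clearly intended. It does not explain why an unchanged 4 should be a failure, or why the two attempts at the same move have different gates.

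A reader might infer more than the text supports:

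- **That the patient is both a success and a failure by definition.** The protocol defines onset of analgesia, not success. The entry gate permits an attempt; it does not promise that rescue will be unnecessary.
- **That the data are beyond repair.** The VAS at positioning is recorded, so failures at exactly 4 can be re-tabulated. Only the fentanyl dose cannot be undone.
- **That the sample-size comparison is damaged.** It rests on the VAS score at positioning, which is recorded whatever the failure label. Failure appears neither in the Objectives nor in the Collecting data list.
- **That about four fentanyl patients would be affected.** That needs whole-number reading, which the protocol does not state, and a model that ignores the repeated test.
- **That the ward rule shows which cut-off was meant.** It is consistent with < 4, but it concerns a different drug, time and purpose.

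**Conclusion.** The point holds as an inconsistency in a stated treatment and classification rule, and it is minor. The comparison of cut-offs needs no assumption: a patient moved at exactly 4 with unchanged pain is a recorded failure and receives 1 mic/kg fentanyl, and first attempt and reattempt use different gates.

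The size does rest on assumptions. With the planning values treated as normal and the line read to the millimetre, it is likely under one patient per group: about 0.5 for fentanyl and 0.1 for fascia iliaca, with no basis for a PENG figure. Whole-number reading could make it larger. The protocol does not allow reliable quantification, and the grading does not depend on these counts.

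**What to change.** Use one cut-off throughout. The preferred change is from ≤ 4 to < 4 in three places: the leg-raise definition of onset, the sentence permitting first positioning, and the onset-time entry under Collecting data. This matches the failure and reattempt rules as they stand. Patients whose pain rises to 4 or more on moving remain failures, as intended.

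The cost is small but real. A patient at exactly 4 waits for a further leg-raise test, already repeated every minute, and has a slightly longer recorded onset time. If pain stays at 4 the wait may be longer, because the protocol sets no maximum wait before positioning. No extra patients are needed, and no sample-size figure changes.

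The alternative is to move failure to > 4 and reattempt to ≤ 4. That edits only Administration of spinal anesthesia and leaves the onset definition intact, but it accepts a score of 4 during the move. Either removes the overlap; the choice is the investigator's.
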